9.4 Primary Clinical Endpoint

The most clinically relevant endpoint for this high-risk SMM population is progression free survival (PFS) as defined by the ASH FDA consensus panel, where failure is defined as death or the appearance of symptomatic myeloma indicating treatment.(64) Following the ASH/FDA consensus, symptomatic MM is present or imminent end-organ damage characterized by hypercalcemia, renal insufficiency, anemia or bone disease related to the plasma cell proliferative process.(64) Our primary analysis is the comparison of progression-free survival (PFS) of high risk SMM patients treated with lenalidomide to those given no treatment. Patients will be randomized in equal proportions to R or Obs. Treatment will be assigned using permuted blocks within strata with dynamic balancing within main institution and their affiliate networks. PFS in each of the arms will be estimated using the method of Kaplan and Meier.(65) PFS between the two arms will be compared using a stratified log-rank test.(66)

Rev. 12/13

It is expected that the median PFS of patients on the Obs arm will be 24.8 months (hazard rate of 0.0279). The study is designed to detect a 60% reduction in hazard rate to 0.011. If PFS follows an exponential distribution, this difference corresponds to a 150% improvement in PFS to a median of 62 months. These rates are derived from studies cited earlier (more specifically a 2-yr progression rate of 41.5% for the obs arm based on the Dispenzieri study)(23), an NIH funded phase III trial of thalidomide plus zoledronic acid versus zoledronic acid alone at the Mayo Clinic and the Spanish SMM study (Mateos et al. Blood 2014). The primary analysis will be intention-to-treat analysis. Accrual duration is estimated at 45 months in order to obtain 180 patients (90 on each arm), and follow patients for an additional 9 months after closure to accrual. At this point, full information which is considered to be when 76 patients have progressed or died will be obtained.

Rev. 1/16

With the expected accrual and failure rates above, the trial will have 96% power, at the one-sided 0.025 significance level, to detect a hazard ratio of 2.5 or more (for Obs versus R). By starting with such high power, the study is designed to accommodate potential treatment non-adherence. For example, if (a random) 5% of the patients on each arm cross over to the opposite treatment, then the ITT hazard ratio would be expected to be about 2.2 (when the true Obs vs R ratio for the full population is 2.5), and the design would still have about 91.1% power, and if 10% of the patients on each arm cross over to the opposite treatment, then the ratio would be decreased to about 1.97, and the ITT analysis would still have at least 78% power.

This design incorporates 5 interim analyses and one final analysis for the PFS comparison. The final analysis will occur at full information (76 patients progressed/died). This study incorporates a group sequential monitoring plan to adjust for sequential testing to stop early in favor of the alternative hypothesis. Once the trial reaches approximately 25% information, one analysis will be performed every 6 months to correspond with the scheduled Data Monitoring Committee (DMC) meeting. Critical values will be determined using a truncated version of the Lan-Demets error spending rate function corresponding to the O'Brien-Fleming boundary.(67) At each interim analysis, the null hypothesis of equal PFS rates on the two arms will be tested against the one-sided alternative of increased PFS on the R arm. The p-value from a one-sided stratified log-rank test will be compared to the critical value. At any of the interim analyses, if the null hypothesis is rejected, the DMC may consider closing the study. The table below gives the expected timing of the analyses and the critical values for rejecting the null hypothesis.

Rev. 12/13

Repeated analysis	Time from Study Start (Months)	Information Time (%)	Failures under the Alternative Hypothesis	Nominal Significance level for Rejecting the Null Hypothesis
1	24	26	20	0.0005
2	30	39	29	0.0005
3	36	53	40	0.0015
4	42	69	52	0.0061
5	48	86	65	0.0130
6	54	100	76	0.0199

Rev. 7/13

In addition to monitoring the study for early stopping in favor of the alternative hypothesis of increased PFS on the R arm, the study will also be monitored for early stopping in favor of the null hypothesis of no significant increase in PFS on the R arm using the repeated confidence interval methodology similar to that described by Jennison and Turnbull.(68) At each interim analysis, a nominal one-sided (1-alpha) confidence interval around the hazard ratio (Obs over R) produced by the Cox proportional hazards model will be computed.(69) The alpha used to compute the confidence interval is the nominal significance level of the use function boundary at the information fraction at the particular analysis time. The target hazard ratio will be adjusted for observed treatment non-adherence. If at any of the analyses the confidence interval does not contain the target hazard ratio, the DMC may consider stopping the trial early for lack of treatment difference.

Rev. 1/16, 1/16

9.5 Secondary Clinical Endpoints

Secondary endpoints for this study include response rate and duration of response among responders. Response rate (CR+PR) on the R arm will be calculated and a 95% confidence interval will be computed around the response rate. The maximum width of a 95% confidence interval around response rate would be 21.5%. Duration of response among responders will be estimated using the Kaplan-Meier method.(65) Cox proportional hazards model will be used to assess PFS outcome in multiple regression analyses of established prognostic factors.(69) Adverse events will be monitored on all patients and summarized by arm. The difference in rates of all Grade 3 or higher toxicities will be evaluated for all randomized patients using the Fisher's Exact Test.

Overall Survival (OS) in each of the arms will be estimated using the method of Kaplan and Meier.(65) OS between the two arms will be compared using stratified log-rank test. (66) Cox proportional hazards model will be used to estimate the hazard rate between arms (69). OS will be evaluated at month 90/ year 7.5 when there is adequate power. The estimated 3-year survival probability on the R arm is supposed to parallel the probability for the general population of persons aged over 65 years (93%). The 3-year survival probability for an untreated high-risk SMM population is estimated at 83%.(23) Assuming exponential distributions, these probabilities correspond to a median OS of 28.7 and 11.2 years. For this analysis, we assume the R treated high-risk SMM population has a slightly inferior hazard of death than the general population: 3-year survival probability of 91% (hazard rate=0.0315). This estimate is

unchanged although the Spanish study reported 93% survival after approximately 5 years of follow-up (Mateos et al. Blood 2014). In the first report (Mateos et al. NEJM 2013), the 3-year survival on the watchful waiting arm of the Spanish study was 80%. In the long-term update, 5-year survival was 67% corresponding to a median OS of 9.2y on the watchful waiting arm. In this redesign, the 3-year OS estimate for the Obs arm was thus reduced to 79%. If OS follows an exponential distribution, this corresponds to medians of 22 years (R) and 8.8 years (Obs). There is 81% power to detect this difference assuming a one-sided 0.025 significance level and 47 events out of n=180 patients at the time of analysis.

Rev. 12/13

Overall Survival (OS) in each of the arms will be estimated using the method of Kaplan and Meier.(65) OS between the two arms will be compared using stratified log-rank test. (66) Cox proportional hazards model will be used to estimate the hazard rate between arms (69). OS will be evaluated at month 90/ year 7.5 when there is adequate power. The estimated 3-year survival probability on the R arm is supposed to parallel the probability for the general population of persons aged over 65 years (93%). The 3-year survival probability for an untreated high-risk SMM population is estimated at 83%.(23) Assuming exponential distributions, these probabilities correspond to a median OS of 28.7 and 11.2 years. For this analysis, we assume the R treated high-risk SMM population has a slightly inferior hazard of death than the general population: 3-year survival probability of 91% (hazard rate=0.0314). This estimate is unchanged and was confirmed with results from the Spanish study [ref]. The 3-year survival probability on the watchful waiting arm of the Spanish study, however, was 67%. Given the Spanish study was comprised of higher risk patients, a 3-year probability of 79% is assumed. If OS follows an exponential distribution, this corresponds to medians of 22 years (R) and 8.8 years (Obs). There is 81% power to detect this difference assuming a one-sided 0.025 significance level and 47 events out of n=180 patients at the time of analysis

Rev. 1/16

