5.1 Administration Schedule

5.1.1 Arm A Lenalidomide*

Lenalidomide 25 mg by mouth days 1-21 every 4 weeks (28 days).

Aspirin (or alternative prophylaxis) days 1-28 for each treatment cycle. Suggested dose is 325 mg/day, however the dose is at the discretion of the treating physician. Alternative dosing of 75mg/day or higher is acceptable provided the patient is at low risk of thrombosis.

All patients on Arm A are required to receive prophylaxis against thrombosis. For patients in Arm A, physicians should consider prophylaxis with aspirin alone as studies with single agent lenalidomide in the setting of relapsed disease show a relatively low incidence of thrombosis (< 5%). See Section [5.5.2.1](#) for acceptable alternative prophylaxis.

Treatment continues until progression to symptomatic myeloma or discontinuation due to toxicity.

For patients with CrCl 30-60 mL per minute, lenalidomide dose is 10 mg per day for days 1-21 every 28 days. Creatinine clearance (CLcr) can either be measured CLcr or estimated by the Cockcroft-Gault method: $\{[140 - \text{age (yrs)}] \times [\text{lesser of IBW (kg) or actual weight (kg)}]\} / [72 \times \text{serum creatinine (mg/dL)}]$; multiply by another factor of 0.85 if female.

* **NOTE:** The first 44 patients to accrue will be placed on Arm A without randomization (Phase II).

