5.1.2 Arm B Observation

Observation continues until progression to symptomatic myeloma.

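### Grade 3 or higher toxicity is compared between arms only by a crude Fisher test, which ignores time at risk; the result should not be read as a comparison of toxicity rates

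*Combined protocol and SAP*

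**What the plan says.** Section 9.5 gives one between-arm safety test: "The difference in rates of all Grade 3 or higher toxicities will be evaluated for all randomized patients", by Fisher's exact test. The only other adverse event analysis there is "Adverse events will be monitored on all patients and summarized by arm". No person-time rate, time-to-event method, analysis date, significance level or collection window is given for this comparison.

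The two arms end as follows. For Arm A (Section 5.1.1), "Treatment continues until progression to symptomatic myeloma or discontinuation due to toxicity". For Arm B (Section 5.1.2), "Observation continues until progression to symptomatic myeloma".

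Section 9.4 expects a median PFS of 24.8 months on observation, and "The study is designed to detect a 60% reduction in hazard rate to 0.011" per month, a median of 62 months on R. It plans 90 patients per arm, 45 months of accrual and 9 more months of follow-up.

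On collection of adverse events, Section 5.2.1 refers routine reporting to the Forms Packet, which is not among the documents. Sections 5.2.4 and 5.2.6 tie expedited reporting to 30 days after the last dose, a reference point that Arm B does not have. Section 5.7 follows patients who stop early until progression, but for response and survival; it does not say that adverse events are collected over that time.

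**The concern.** A Fisher test on all randomized patients treats each patient as having had the same opportunity to record an event. The design expects the opposite: progression or death is assumed to be 2.5 times slower on R, so if events are recorded until progression, R patients are watched longer. Two arms with the same toxicity rate would then show different proportions.

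What is at stake is interpretation. Patients are asymptomatic and the control is no therapy. Section 1.5 itself says that a PFS gain has to be weighed against the costs and side effects of treatment. If the only planned toxicity comparison mixes toxicity with length of observation, that weighing has a weaker basis than it needs.

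**Working it through.** **Inputs.** From Section 9.4: exponential PFS with medians of 24.8 months (Obs) and 62 months (R), so h = ln 2/24.8 = 0.02795 and ln 2/62 = 0.01118 per month; 90 per arm; 45 months of accrual, taken as uniform; cutoff at month 54. Assumed: a constant grade 3 or higher hazard a, the same in both arms, of 5, 10 or 20% per year (0.00417, 0.00833 or 0.01667 per month). Also assumed: the toxicity analysis is done at month 54.

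**Reproducing the plan.** Follow-up runs from 9 to 54 months. The mean event-free probability is S(k) = [exp(-9k) - exp(-54k)]/(45k).
- Obs: S = 0.4425, so 90 x 0.5575 = 50.2 events.
- R: S = 0.7106, so 90 x 0.2894 = 26.0 events.
- Total 76.2, against 76 stated. With the rounded hazards 0.0279 and 0.011 the total is 75.8.

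**Mean time at risk if collection runs to progression.** (1 - S(h))/h:
- Obs: 0.5575/0.02795 = 19.9 months.
- R: 0.2894/0.01118 = 25.9 months, a ratio of 1.30.

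**Proportion ever affected with identical toxicity hazards.** a/(a+h) x [1 - S(a+h)]. At 10% per year:
- Obs: 0.2297 x (1 - 0.3555) = 14.8%.
- R: 0.4271 x (1 - 0.5584) = 18.9%.

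| Common rate per year | Obs | R | Gap (points) | Fisher rejects |
|---|---|---|---|---|
| 5% | 7.8% | 10.1% | 2.2 | about 5% |
| 10% | 14.8% | 18.9% | 4.1 | about 8% |
| 20% | 26.6% | 33.3% | 6.7 | about 13% |

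The last column is exact enumeration with 90 per arm at two-sided 0.05. That level is an assumption. With truly equal proportions this test rejects in about 3-4% of trials.

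If collection to progression continued to month 90, when OS is analysed, the proportions would be 11.4% vs 17.3%, 20.8% vs 30.9% and 35.2% vs 50.1% (Obs vs R).

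**If collection ends when lenalidomide stops.** Add a constant stopping rate d on R for reasons other than progression. Times at risk are equal when d is the difference in hazards, 0.0279 - 0.011 = 0.0169, about 0.017 per month. At d = 0.03 the mean time on R is 16.7 months against 19.9 on Obs, and the 10% case becomes 12.5% on R against 14.8% on Obs.

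**If the window is short and fixed.** Every patient has at least 9 months of potential follow-up, so for a 6-month window the proportion is a/(a+h) x [1 - exp(-6(a+h))]. At 10% per year this is 4.5% (Obs) vs 4.7% (R). Even at 20% per year it is 8.8% vs 9.2%.

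**Which alternatives remove the dependence.** In 20,000 simulated trials per setting with equal hazards of 0.01 to 0.05 per month, at months 54 and 90, a log-rank test on time to first event, censored at progression or cutoff, rejected in 4.8-5.3%. An exact person-time comparison rejected in 3.4-4.3%.

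Cumulative incidence with progression and death as competing events does not remove it. By time u it equals a/(a+h) x [1 - exp(-(a+h)u)], which still contains h. At 10% per year it gives 13.4% (Obs) vs 16.0% (R) at 24 months and 16.7% vs 21.6% at 36 months. The 36-month gap, 4.8 points, exceeds the crude gap of 4.1.

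**The case against.** The strongest objection is that the documents say when treatment and observation end, not when adverse event collection ends. This stands. The 2-7 point figure is conditional on collection to progression and a month-54 cutoff.

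Second, the proportion of randomized patients ever affected is a legitimate measure of a treat-until-progression strategy. This also stands. A reader might infer that the Fisher result says nothing about the drug's toxicity. That goes too far: at 5-20% per year and month 54 the test rejects in about 5-13% of trials with equal rates, which is inflated but limited.

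Third, if the word toxicities in Section 9.5 means events attributed to treatment, the observation rate is near zero and the equal-rates calculation does not apply. Section 9.5 does not say which is meant. Even then, the size of the R proportion would depend on how long R patients are observed.

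Fourth, person-time rates have a weakness of their own. If toxicity is front-loaded, long later exposure on R dilutes a single overall rate in the drug's favour. This is a reason to split the rate by period.

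Finally, this is a secondary comparison with no stated power or decision rule, and the DMC reviews safety twice a year (Section 9.10). That limits the weight of the point but does not make the crude comparison easier to interpret.

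**Conclusion.** The point holds in a limited form. The only planned between-arm toxicity test ignores time at risk, and the plan's own PFS assumptions make time at risk unequal if events are collected to progression: 25.9 vs 19.9 months at month 54. Identical rates of 5-20% per year would then look like a 2-7 point excess on R.

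A reader might infer that the planned test necessarily overstates lenalidomide's toxicity. The documents do not support a fixed direction. About 0.017 per month of other stopping on R, with collection ending at stopping, cancels the gap, and 0.03 per month reverses it. A window of about 6 months makes it negligible.

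The conclusion rests on exponential PFS at the design values, uniform accrual, and constant, equal toxicity hazards, which are assumed because the documents give none. The PFS test and its error rate are unaffected.

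**What to change.** In Section 9.5:

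1. State one adverse event collection window that applies to both arms, the analysis cutoff, and whether the comparison covers all events or only those attributed to treatment.
2. Add grade 3 or higher events per 100 patient-months by arm with 95% confidence intervals, split by period, for example the first 6 cycles (the period used for the phase II toxicity endpoint in Section 9.3) and later.
3. Compare time to first grade 3 or higher event by a cause-specific hazard analysis (log-rank or Cox), censoring at progression, death or end of collection.
4. Do not use a cumulative-incidence comparison as the correction, because it depends on progression in the same way.
5. Keep the Fisher test and the crude table, labelled as description of the whole strategy.

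The cost is one more table and the assumption that censoring at progression or end of collection is non-informative. The analysis needs event onset dates and end-of-collection dates; the forms are not in the documents, so confirm that these are recorded. Design, sample size and patient management do not change. Label: cheap improvement.

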9.6 Stem Cell Mobilization

Patients are recommended to undergo stem cell mobilization with growth factors following 4 to 6 cycles of therapy. Successful mobilization defined as collection of 5×10^6 cd34 cells per kilogram weight is an important outcome for patients treated with lenalidomide treatment. A growth factor mobilization failure rate of 10% is considered acceptable and a rate of 25% or less is unacceptable. Assuming 60% of patients on the lenalidomide arm opt for stem cell growth factor mobilization then there will be approximately 54 evaluable patients. An early stopping rule on the first 13 evaluable patients will be imposed. With 13 evaluable patients, if 3 or more patients fail, the study team will consider stopping this trial for an unacceptable growth factor mobilization failure rate. With this design based on exact binomial distribution, the probability of stopping early is 67% if the true but unknown failure rate is 25%, and 13% if the true rate is 10%.

9.7 Quality of Life

9.7.1 Primary QOL Endpoints

Quality of life assessment is performed in an identical fashion in both arms A and B and will be administered to both arms on the same schedule and frequency. The QOL assessment utilizing the FACT-

FWB+PWB and MMS instruments will first be administered at registration (+ 7 days) prior to initiation of treatment or observation. During the treatment or observation period, QOL will be measured every 6 cycles (day end + 7 days) and at the end of treatment or observation (+ 14 days). For patients that discontinue protocol therapy or go off observation early not due to disease progression, QOL will also be assessed at the next quarterly Long Term follow-up visit (+ 14 days). After this, these patients will not be followed further for QOL. Patients will be asked to complete the QOL questionnaire just prior to meeting with health care providers at scheduled visits. This should reduce the impact of health care related information upon perceived QOL.

The FACT-FWB+PWB PRO instrument has 14 items and the score ranges from 0-56. The primary endpoint for the QOL study will be defined as the mean change of the FACT-FWB+PWB score from registration (prior to randomization) to cycle 24. The null hypothesis is that the FACT-FWB+PWB mean change score between the two groups is the same over this time period. Based on the length of this PRO instrument, a minimal absolute difference in means change scores of the two arms of 4-6 is considered clinically significant between two groups.(70) Nevertheless, for this analysis the difference in drug-related QOL must be much greater to overcome a significant PFS benefit. The FACT- FWB+PWB domains are reported to have a standard deviation (SD) of 11. (Personal Correspondence with [name] dtd 12.26.08)

Differences in FACT-FWB+PWB mean change scores between the treatment arms from time of registration to cycle 24 that can be detected with 80% power are presented in following table. The expected hazard rates on each arm served to establish patients alive without PD at the end of the interval. Sensitivity for the % of patients alive without PD (n=55 patients given expected hazard rates) assumed to complete the questionnaire at the end of cycle 24 (compliance rates of 55%, 70%, 85%), allowing for slightly more variability in the instrument (11.0, 12.0) and assuming different correlation (0.4, 0.6, 0.8) between repeated measures was performed. For example, assuming a SD of 11.0 for the FACT-FWB+PWB, a correlation between repeated measures of 0.6 and using a two-sided t-test with a 0.05 significance level, there is sufficient power to detect a true difference in the FACT-FWB+PWB mean change score between the two arms of 7.3-9.2. Given our chosen interval for the primary endpoint and the reduced sample size with the redesign, we will only be able to detect large differences in mean change score between arms at expected compliance rate (70%).

Differences detected with 80% power between Treatment Arms in Mean Change Score from Registration to end of Cycle 24: FACT-FWB+PWB					
standard deviation (SD)	correlation	SD of change	55% compliance n=30	70% compliance n=38	85% compliance n=56
11.0	0.4	12.05	11.2	9.9	9.0
	0.6	9.84	9.2	8.1	7.3
	0.8	6.96	6.5	5.7	5.2
12.0	0.4	13.15	12.2	10.8	9.8
	0.6	10.73	10.0	8.8	8.0
	0.8	7.59	7.1	6.2	5.7

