2.3 Quality of Life Assessment Objectives

- 2.3.1 To compare QOL change between treatment and observation arms based on the functional (FWB) and physical (PWB) well-being components of the FACT-General (G) patient-reported outcome (PRO) measure from registration (prior to initiation of treatment) up to cycle 24.
- 2.3.2 To examine the impact of differential treatment response (PFS), if observed, on QOL based on the FACT FWB+PWB up to cycle 48.
- 2.3.3 To obtain prospective data on Myeloma specific QOL attributes, utilizing and evaluating the Multiple Myeloma Subscale (MMS).

3. Selection of Patients

Each of the criteria in the checklist that follows must be met in order for a patient to be considered eligible for this study. Use the checklist to confirm a patient's eligibility. For each patient, this checklist must be photocopied, completed and maintained in the patient's chart.

In calculating days of tests and measurements, the day a test or measurement is done is considered Day 0. Therefore, if a test is done on a Monday, the Monday four weeks later would be considered Day 28.

ECOG-ACRIN Patient No. _____

Patient's Initials (L, F, M) _____

Physician Signature and Date _____

NOTE: All questions regarding eligibility should be directed to the study chair or study chair liaison.

NOTE: Institutions may use the eligibility checklist as source documentation if it has been reviewed, signed, and dated prior to registration/randomization by the treating physician.

Rev. 7/14

NOTE: This study involves pre-registration (see Section 4). Bone marrow and peripheral blood specimens are to be submitted for defined laboratory research studies and future undefined research studies as outlined in Section 10 per patient consent.

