4.5 Stratification Factors

Rev. 12/13

4.5.1 Time Since Smoldering Multiple Myeloma Diagnosis: 1 year vs. > 1 year.

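### Section 9.7.1 sizes the primary QOL comparison on the unadjusted change score; adjusting for the baseline score already collected would sharpen it modestly at almost no cost

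*Combined protocol and SAP*

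**What the plan says.** Section 2.3 sets the QOL aim: "To compare QOL change between treatment and observation arms". Section 9.7.1 makes it specific: "The primary endpoint for the QOL study will be defined as the mean change of the FACT-FWB+PWB score from registration" to cycle 24, with a null hypothesis of equal mean change in the two arms. No covariate is mentioned.

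The sizing table uses an SD of 11 or 12, correlations of 0.4, 0.6 and 0.8, and compliance of 55%, 70% and 85% among 55 patients alive without progression at the end of cycle 24. The worked example is computed "using a two-sided t-test with a 0.05 significance level", and no sentence states the final model. The analysed set is defined by survival without progression: "The expected hazard rates on each arm served to establish patients alive without PD at the end of the interval".

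On interpretation, the section says that "a minimal absolute difference in means change scores of the two arms of 4-6 is considered clinically significant". It then adds that, for this analysis, the difference would have to be much greater to outweigh a PFS benefit. It concedes that after the redesign only large differences are detectable at the expected 70% compliance.

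Elsewhere the plan does use its design factor. Section 4.5 stratifies by "Time Since Smoldering Multiple Myeloma Diagnosis: 1 year vs. > 1 year", and Section 9.4 states that "PFS between the two arms will be compared using a stratified log-rank test". Section 9.7.2 names a mixed model and joint dropout models, but for the secondary comparison of patients with and without progression.

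**The concern.** A t-test on change fixes the slope of the cycle-24 score on baseline at 1. ANCOVA estimates that slope. When baseline and follow-up are only moderately correlated, fixing it at 1 adds noise that could be removed with data already in hand. The comparison has few evaluable patients and, by the plan's own account, limited sensitivity, so a cheap gain in precision is worth having. Naming the model in advance also settles which result is primary before the data are seen.

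**Working it through.** **1. Confirm what was sized.** Section 9.7.1 gives SD s (11 or 12) and correlation r. With SD of change = s·√(2(1−r)):
- s = 11: 12.05, 9.84, 6.96 at r = 0.4, 0.6, 0.8
- s = 12: 13.15, 10.73, 7.59

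All six printed values reproduce. The sizing therefore uses the unadjusted change score with the same SD at both times.

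**2. Reproduce the printed detectable differences.** At SD 11 and r = 0.6 the plan prints 9.2 / 8.1 / 7.3 for 55 / 70 / 85% compliance. With 80% power and the noncentral t:
- two-sided 0.05, n = 30 / 38 / 46 in total: 10.4 / 9.2 / 8.3
- two-sided 0.05, the same n per arm: 7.2 / 6.4 / 5.8
- one-sided 0.05, n in total: 9.2 / 8.1 / 7.3

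Only the one-sided calculation matches, and it does so in all 18 cells of the table. The 85% column is headed n=56, but 85% of 55 is 46.75 and its values match 46.

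**3. Gain from baseline adjustment.** Let k be the cycle-24 SD divided by the baseline SD.
- Var(change) = s²(1 + k² − 2rk)
- ANCOVA residual variance = s²k²(1 − r²)
- Difference = s²(rk − 1)², which is never negative

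At k = 1 the ratio is (1 + r)/2 = 0.70 / 0.80 / 0.90, a reduction of 30 / 20 / 10%. At s = 11 the residual SDs are 10.08 / 8.80 / 6.60.

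The documents give no cycle-24 SD, so k is an assumption. The range is:

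| k | r = 0.4 | r = 0.6 | r = 0.8 |
|---|---|---|---|
| 0.9 | 38% | 29% | 21% |
| 1.0 | 30% | 20% | 10% |
| 1.1 | 24% | 13% | 3% |
| 1.25 | 16% | 6% | 0% |

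**4. Cost of estimating the slope.** The percentages in step 3 are residual-variance figures. In simulation with 19 per arm and k = 1, the net reduction in the variance of the arm difference was about 28 / 17 / 7%. With the stratum also in the model it was about 15–16% at r = 0.6.

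**5. Detectable difference** (SD 11, r = 0.6, k = 1, 70% compliance, 80% power):

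| Reading of n | Test | Change score | ANCOVA |
|---|---|---|---|
| 38 in total | two-sided 0.05 (as stated) | 9.2 | 8.2 |
| 38 in total | one-sided 0.05 (matches table) | 8.1 | 7.2 |
| 38 per arm | two-sided 0.05 | 6.4 | 5.7 |

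The ANCOVA column charges the lost degrees of freedom but not slope estimation. Charging that too, the first row becomes about 8.23 × √(0.83/0.80) = 8.4. With k = 1.25 the first row would be 10.6 to 10.3.

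**6. Which reading of n.** Section 9.7.1 does not say whether 55 is a total or per arm. Twenty-four 28-day cycles are 22.1 months. With the Section 9.4 medians, patients alive without progression would number 90·exp(−(ln 2/24.8)·22.1) = 48.6 on observation and 90·exp(−(ln 2/62)·22.1) = 70.3 on lenalidomide. At 70% compliance that is 34 and 49, and the two-sided detectable difference falls from 6.2 to 5.6.

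**7. Power at 6 points, for illustration only** (two-sided, r = 0.6, slope estimation not charged): 45% to 53% with 38 in total, and 75% to 84% with 38 per arm. With slope estimation and the stratum included, simulation put the first gain at 45% to 51%.

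**The case against.** **Six points is not the decision threshold.** This stands. Section 9.7.1 says the difference must be much greater for this analysis and gives no figure. If 9 points is assumed (SD 11, r = 0.6, two-sided), power rises only from 97.6% to 99.3% with 38 per arm, though from 78% to 86% with 38 in total. The case for adjustment is therefore a narrower confidence interval at any threshold, not power at 6.

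**The sizing discrepancy matters more than the adjustment.** This largely stands. Depending on sidedness and the reading of n, the unadjusted figure for one cell runs from 6.4 to 9.2. On the stated two-sided test with 38 in total, the adjusted 8.2 is no better than the printed 8.1. The table has to be reconciled in any case.

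**ANCOVA may answer a different question here.** This stands in part. Only cycle-24 completers alive without progression are compared, so randomization does not guarantee equal baselines among them. Suppose completers' mean baselines differ by 3 points (an assumption) with equal true mean change. At r = 0.6 ANCOVA then estimates (1 − 0.6) × 3 = 1.2 points. In simulation with 34 and 49 patients it rejected 9% of the time, against 5% for the change score. Other dropout patterns could favour ANCOVA. This is a reason to report both, not to leave baseline unused.

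**The t-test appears only in a sizing example.** True. A reader might infer that the plan commits to an unadjusted final analysis, but the documents do not say so. They leave the primary model unnamed.

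**Nothing shows that time since diagnosis predicts QOL.** Also true. No gain from the stratum is counted above.

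**Conclusion.** The point holds as a modest efficiency improvement. Under the plan's equal-SD assumption, baseline adjustment lowers residual variance by 30 / 20 / 10% at r = 0.4 / 0.6 / 0.8. The net figure is about 28 / 17 / 7% if 38 is the total. At r = 0.6 the residual-variance gain shrinks to 6% if the cycle-24 SD is 1.25 times baseline. With k = 1, the detectable difference at SD 11 and r = 0.6 drops by roughly 0.7 to 1.0 points, depending on the reading of n and the sidedness.

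Two stronger readings are not supported. A reader might infer that the change-score t-test is invalid or biased. It is a valid test of the stated null, and no bias of known size or direction is shown. A reader might also infer that adjustment would repair selective dropout among completers. It would not.

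**What to change.** In Section 9.7.1, name as the primary QOL analysis an ANCOVA of the cycle-24 FACT-FWB+PWB score (equivalently, of the change) on arm, adjusted for the baseline score and the time-since-diagnosis stratum. Keep the change-score t-test as a supportive analysis and report both, noting that they can target different contrasts if completers' baselines differ by arm. State whether the joint dropout model in Section 9.7.2 also covers the arm contrast at cycle 24.

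When restating the detectable differences, say whether n is a total or per arm, reconcile the table with the stated two-sided test, and correct or explain the n=56 heading.

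The cost is a few sentences, one or two degrees of freedom and the small loss from estimating the slope. No new data or visits are needed.
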